### 11.3.7.1 Estimands for continuous endpoints

The primary and hypothetical supplementary estimands for continuous endpoints, which differ only in handling of the missing data, attempt to quantify the effect of treatment, in the hypothetical scenario, where subjects do not permanently discontinue IMP for any reason and where rescue treatment is not made available.

The estimands are described by the following attributes:

- Target Population: Subjects with moderate-to-severe AD, as defined through the inclusion and exclusion criteria listed in Section 5.
- Variable: Applied to continuous endpoints.
- Treatment conditions: LEO 138559 dose regimens 1-4 versus placebo.
- Strategies for handling intercurrent events:

THIS DOCUMENT CONTAINS CONFIDENTIAL INFORMATION AND MUST NOT BE COPIED OR MADE AVAILABLE TO ANY THIRD PARTY WITHOUT THE PRIOR WRITTEN CONSENT OF THE LEO PHARMA GROUP

- a. For subjects requiring the use of rescue treatment or permanently discontinuing IMP, the hypothetical strategy will be used to estimate the treatment effect in the hypothetical scenario where rescue treatment is not available, and where subjects do not permanently discontinue IMP for any reason.
- E. Population level summary: Difference in means between the treatment conditions.

### Second supplementary estimand

The second supplementary estimand for continuous endpoints attempts to quantify the effect of the decision to treat subjects with the randomized treatment, ignoring the occurrence of intercurrent events.

The estimand is described by the following attributes:

- A. Target Population: Subjects with moderate-to-severe AD, as defined through the inclusion and exclusion criteria listed in Section 5.
- B. Variable: Applied to percent EASI change from baseline endpoints.
- C. Treatment conditions: LEO 138559 dose regimens 1-4 versus placebo.
- D. Strategies for handling intercurrent events
  - a. The treatment policy strategy will be used to handle the initiation of rescue treatment or permanent discontinuation of IMP. Data observed after the occurrence of such events will be included in the analysis.
- E. Population level summary: Difference in means between the treatment conditions.

#### 11.3.7.2 Estimands for binary endpoints

The primary estimand for binary endpoints attempts to quantify the effect of treatment in the hypothetical scenario where:

- All subjects remain on treatment except for those permanently discontinuing IMP due to lack of efficacy or the occurrence of an AE related to worsening of AD. AEs considered related to worsening of AD will be specified in the SAP.

The occurrence of the following intercurrent events will be treated as indicating a failure of the randomized treatment:

THIS DOCUMENT CONTAINS CONFIDENTIAL INFORMATION AND MUST NOT BE COPIED OR MADE AVAILABLE TO ANY THIRD PARTY WITHOUT THE PRIOR WRITTEN CONSENT OF THE LEO PHARMA GROUP

- Permanent discontinuation of IMP due to lack of efficacy or the occurrence of an AE related to worsening of AD.
- Initiation of rescue treatment.

The estimand is described by the following attributes:

- A. Target Population: Subjects with moderate-to-severe AD, as defined through the inclusion and exclusion criteria listed in Section 5.
- B. Variable: Applied to binary endpoints.
- C. Treatment conditions: LEO 138559 dose regimens 1-4 versus placebo.
- D. Strategies for handling intercurrent events
  - a. Subjects initiating rescue treatment or permanently discontinuing IMP due to lack of efficacy or the occurrence of an AE related to worsening of AD are defined as treatment failures according to the composite strategy.
  - b. For subjects permanently discontinuing IMP due to reasons other than lack of efficacy or the occurrence of an AE related to worsening of AD, the hypothetical strategy will be used to estimate the effect of treatment in the hypothetical scenario where subjects do not permanently discontinue IMP for reasons other than lack of efficacy or the occurrence of an AE related to worsening of AD.
- E. Population level summary: Difference in response rates between the treatment conditions.

### Supplementary estimand

The supplementary estimand for binary endpoints attempts to quantify the effect of the decision to treat subjects with the randomized treatment, ignoring the occurrence of intercurrent events.

The estimand is described by the following attributes:

- A. Target Population: Subjects with moderate-to-severe AD, as defined through the inclusion and exclusion criteria listed in Section 5.
- B. Variable: Applied to EASI, vIGA-AD and ADSD Worst █ responder endpoints.

THIS DOCUMENT CONTAINS CONFIDENTIAL INFORMATION AND MUST NOT BE COPIED OR MADE AVAILABLE TO ANY THIRD PARTY WITHOUT THE PRIOR WRITTEN CONSENT OF THE LEO PHARMA GROUP

C. Treatment conditions: LEO 138559 dose regimens 1-4 versus placebo.

D. Strategies for handling intercurrent events:

- a. The treatment policy strategy will be used to handle the initiation of rescue treatment or permanent discontinuation of IMP. Data observed after the occurrence of such events will be included in the analysis.

E. Population level summary: Difference in response rates between the treatment conditions.

#### **11.3.7.3 Estimands for time-to-event endpoints**

The primary estimand for the time-to-event endpoint, time from baseline to the initiation of rescue treatment, quantifies the effect of treatment while subjects are receiving treatment.

The estimand is described by the following attributes:

- A. Target Population: Subjects with moderate-to-severe AD, as defined through the inclusion and exclusion criteria listed in Section 5.
- B. Variable: Time from baseline to the initiation of rescue treatment.
- C. Treatment conditions: LEO 138559 dose regimens 1-4 versus placebo.
- D. Strategies for handling intercurrent events:
  - a. Subjects permanently discontinuing IMP are considered to have experienced a competing risk, i.e. no longer considered at risk for initiating rescue treatment, in line with the while on treatment strategy.
- E. Population level summary: Difference in the cumulative incidence of initiation of rescue treatment at Week 16 between the treatment conditions.

#### **Supplementary estimand**

The supplementary estimand assesses the effect of the treatment on the composite endpoint, time from baseline to the initiation of rescue treatment or permanent discontinuation of IMP, whichever occurs first.

The estimand is described by the following attributes:

THIS DOCUMENT CONTAINS CONFIDENTIAL INFORMATION AND MUST NOT BE COPIED OR MADE AVAILABLE TO ANY THIRD PARTY WITHOUT THE PRIOR WRITTEN CONSENT OF THE LEO PHARMA GROUP

- A. Target Population: Subjects with moderate-to-severe AD, as defined through the inclusion and exclusion criteria listed in Section 5.
- B. Variable: Time from baseline to the initiation of rescue treatment or permanent discontinuation of IMP, whichever occurs first.
- C. Treatment conditions: LEO 138559 dose regimens 1-4 versus placebo.
- D. Strategies for handling intercurrent events:
  - a. For subjects who permanently discontinue IMP prior to the initiation of rescue treatment, the event-time is taken as the time of permanent discontinuation of IMP according to the composite time to event variable defined above.
- E. Population level summary: Difference in the cumulative incidence at Week 16 between the treatment conditions.

#### 11.3.7.4 Baseline subgroup estimands

The baseline subgroup estimands are identical to the primary binary estimand but restricted to subgroups, and are described by the following attributes:

- A. Target Population: Subjects with moderate-to-severe AD, as defined through the inclusion and exclusion criteria listed in Section 5 with:
  - a. Having a weekly average ADSD Worst █ score of  $\geq 4$  at baseline.
  - b. Having a DLQI score of  $\geq 4$  at baseline.
  - c. Having a POEM score of  $\geq 4$  at baseline
- B. Variable:
  - a. Reduction of ADSD Worst █ score (weekly average)  $\geq 4$  from baseline to Week 16.
  - b. Reduction of DLQI  $\geq 4$  from baseline to Week 16.
  - c. Reduction of POEM score  $\geq 4$  from baseline to Week 16.
- C. Treatment conditions: LEO 138559 dose regimens 1-4 vs placebo.
- D. Strategies for handling intercurrent events:

THIS DOCUMENT CONTAINS CONFIDENTIAL INFORMATION AND MUST NOT BE COPIED OR MADE AVAILABLE TO ANY THIRD PARTY WITHOUT THE PRIOR WRITTEN CONSENT OF THE LEO PHARMA GROUP

- a. Subjects initiating rescue treatment or permanently discontinuing IMP due to lack of efficacy or the occurrence of an AE related to worsening of AD are defined as treatment failures according to the composite strategy.
- b. For subjects permanently discontinuing IMP due to reasons other than lack of efficacy or the occurrence of an AE related to worsening of AD, the hypothetical strategy will be used to estimate the effect of treatment in the hypothetical scenario where subjects do not permanently discontinue IMP for any reason.

E. Population level summary: Difference in response rates between the treatment conditions.

### 11.3.8 Primary estimand analysis

#### 11.3.8.1 Analysis of primary estimand for continuous endpoints

##### Primary analysis

Data collected after permanent discontinuation of IMP or after initiation of rescue treatment will be excluded from the analysis and “treated as missing”. Missing data and data “treated as missing” will be split into two groups:

1. Data “treated as missing” due to permanent discontinuation of IMP due to lack of efficacy, an AE related to worsening of AD, or rescue treatment.
2. Missing data or data “treated as missing” for other reasons than permanent discontinuation of IMP due to lack of efficacy, an AE related to worsening of AD, or rescue treatment.

The first group will have their missing values imputed using last observation carried forward. This reflects an assumption that subjects that need rescue treatment or permanently discontinue IMP due to lack of efficacy or an AE related to worsening of AD must be expected not to improve going forward even if they had continued IMP.

The second group will be imputed using MI (100 iterations) under a MAR assumption within each treatment group. All subject-level data observed prior to the occurrence of an intercurrent event will be used to inform the imputation models. Further details regarding the specification of the imputation models, including choice of seed, will be specified in the SAP.

The imputed datasets will be combined to create 100 complete datasets. For each of the 100 complete datasets, the response will be analyzed using an ANCOVA model adjusted for treatment, baseline disease severity (baseline vIGA-AD score), region (Japan, Other

THIS DOCUMENT CONTAINS CONFIDENTIAL INFORMATION AND MUST NOT BE COPIED OR MADE AVAILABLE TO ANY THIRD PARTY WITHOUT THE PRIOR WRITTEN CONSENT OF THE LEO PHARMA GROUP

countries), and prior use of biologics or systemic JAK inhibitors for AD (Yes/No). The model will also be adjusted for the baseline value of the dependent variable.

The pooled estimate of the difference in the LSmean change from baseline, along with the associated 95% CIs and nominal p-values will be presented. Inference will be based on applying Rubin's rules to the estimates and standard errors from the ANCOVA analysis of the imputed datasets.

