The covariance matrices for the 5 dose regimens in the simulation were assumed to be equal and have a compound symmetry structure with variances equal to 111.0 and covariances equal to 32.5.

The third step was to ensure that the underlying EASI scores from Week 1 to 16 were within the range of the EASI score scale, which runs from [0,72]. This implies natural bounds for the individual simulated changes from baseline in EASI score, as they must lie within the interval, [-baseline score, 72-baseline score].

The final step was to derive the percent change from baseline in EASI score from Week 1 to Week 16, by dividing the simulated changes in baseline in EASI score from Week 1 to 16 by the subject's baseline EASI score.

The simulation further assumed that percentage of subjects withdrawing or experiencing an intercurrent event by Week 16 in dose regimens 1-4 and placebo arms are 20%, 20%, 30%, 40%, and 40%, respectively, the timing of which was assumed to be exponentially distributed.

To approximate the power, 1,000 data sets with 250 subjects were generated based on the randomization scheme. For each data set, 100 complete versions were generated by imputing missing data separately for each treatment arm. The baseline and all post-baseline EASI assessments were included in the imputation model. The imputed data sets were analyzed based on an ANCOVA model. The pooled estimate of the difference in the LSmean change from baseline, along with the associated 95% Cis and nominal p-values, were derived for each simulated data set by applying Rubin's rules to the estimates and standard errors from the ANCOVA analysis of the imputed datasets.

**Panel 15** provides the nominal power as well as the prioritized power based on the hierarchical testing procedure, to reject the null hypotheses testing the LEO 138559 dose regimens 1-4 versus placebo, with respect to the differences in the mean percent change in EASI score from baseline to Week 16.

THIS DOCUMENT CONTAINS CONFIDENTIAL INFORMATION AND MUST NOT BE COPIED OR MADE AVAILABLE TO ANY THIRD PARTY WITHOUT THE PRIOR WRITTEN CONSENT OF THE LEO PHARMA GROUP

**Panel 15: Approximate nominal and prioritized power for rejecting the null hypotheses including in the testing hierarchy, based on the results of the simulation**

Hypothesis	Nominal power	Prioritized power
Dose regimen 1 vs Placebo	~100%	~100%
Dose regimen 2 vs Placebo	99.1%	~99.1%
Dose regimen 3 vs Placebo	97.2%	~96.4%

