### 11.3.6 Testing strategy

The following hierarchical procedure will be used to ensure strong control of the familywise error rate at the 5% significance level (two-sided significance tests), when testing the null hypotheses associated with the primary endpoint, percent change in EASI score from baseline to Week 16:

1. LEO 138559 [REDACTED] mg SC Weeks 0, 1, 2, 3 and then [REDACTED] mg Q2W from Week 4 (dose regimen 1) versus placebo.
2. LEO 138559 [REDACTED] mg SC Weeks 0, 1, 2 and then [REDACTED] mg Q2W from Week 4 (dose regimen 2) versus placebo.
3. LEO 138559 [REDACTED] mg SC Weeks 0 and 2 and then [REDACTED] mg Q2W from Week 4 (dose regimen 3) versus placebo.
4. LEO 138559 [REDACTED] mg SC Weeks 0 and 2 and then [REDACTED] mg Q2W from Week 4 (dose regimen 4) versus placebo.

Under the hierarchical procedure, the first null hypothesis (the difference in the mean percent change in EASI score from baseline to Week 16 between dose regimen 1 and placebo is equal to 0), is tested at the 5% significance level. If that null hypothesis is rejected, the procedure will proceed to test null hypothesis 2 at the 5% significance level. However, if the first null hypothesis cannot be rejected, the procedure stops and null hypotheses 2-4 will not be formally tested. The procedure continues in this fashion, until it either encounters a null hypothesis that cannot be rejected, or all null hypotheses have been rejected. For the purposes of the hierarchical testing procedure, the hypothesis tests will be based on the analysis of the primary estimand for the primary endpoint.

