### Description of intercurrent events

An intercurrent event refers to a post-baseline event that affects either the interpretation or the existence of the measurements of an endpoint. For the purposes of this trial, we define the following 2 intercurrent events:

- ***Initiation of rescue treatment:*** This event occurs when a subject initiates rescue treatment as listed in no. 1-6 of Section 6.7 for intolerable AD signs and/or symptoms. The timing of the event will be taken as the date of initiation of the rescue treatment recorded in the eCRF.
- ***Permanent discontinuation of IMP:*** This event occurs when a subject permanently discontinues IMP. This event can occur either at the subject's own initiative or at the investigator's or sponsor's discretion. The timing of the event will be taken as the date of permanent discontinuation of IMP as recorded in the eCRF.

[Panel 16](#) provides an overview of the estimand strategies defined in Sections 11.3.7.1, 11.3.7.2, and 11.3.7.3 that will be used to address occurrences of the intercurrent events described above.

An overview of statistical analysis of endpoints can be found in [Panel 17](#).

THIS DOCUMENT CONTAINS CONFIDENTIAL INFORMATION AND MUST NOT BE COPIED OR MADE AVAILABLE TO ANY THIRD PARTY WITHOUT THE PRIOR WRITTEN CONSENT OF THE LEO PHARMA GROUP

**Panel 16: Handling of observed and missing data according to intercurrent events in the primary analysis of the estimands defined in Sections 11.3.7.1, 11.3.7.2, and 11.3.7.3**

Events	Observed data or missing	Continuous endpoints			Binary endpoints		TTE endpoints
		Primary Estimand	Hypothetical Suppl. Estimand	Second Suppl. Estimand	Primary Estimand	Suppl. Estimand	
Initiation of rescue treatment	Observed	Treated as missing, MI	Treated as missing, MI	Value will be used as observed	NRI	Value will be used as observed	Not applicable
	Missing	MI	MI	MI	NRI	MI	Not applicable
Permanent discontinuation of IMP, for reasons other than lack of efficacy or an AE related to worsening of AD	Observed	Treated as missing, MI	Treated as missing, MI	Value will be used as observed	Treated as missing, MI	Value will be used as observed	Accounted for as a competing risk a
	Missing	MI	MI	MI	MI	MI	Accounted for as a competing risk a

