Permanent discontinuation of IMP, due to lack of efficacy or an AE related to worsening of AD	Observed	Treated as missing, LOCF	Treated as missing, MI	Value will be used as observed	NRI	Value will be used as observed	Accounted for as a competing risk a
	Missing	LOCF	MI	MI	NRI	MI	Accounted for as a competing risk a

THIS DOCUMENT CONTAINS CONFIDENTIAL INFORMATION AND MUST NOT BE COPIED OR MADE AVAILABLE TO ANY THIRD PARTY WITHOUT THE PRIOR WRITTEN CONSENT OF THE LEO PHARMA GROUP

Events	Observed data or missing	Continuous endpoints			Binary endpoints		TTE endpoints
		Primary Estimand	Hypothetical Suppl. Estimand	Second Suppl. Estimand	Primary Estimand	Suppl. Estimand	
No intercurrent events	Observed	Value will be used as observed	Value will be used as observed	Value will be used as observed	Value will be used as observed	Value will be used as observed	Not applicable
	Missing	MI	MI	MI	MI	MI	Not applicable

a) Withdrawal from trial will also be accounted for as a competing risk.

**Abbreviations:** AD = atopic dermatitis; AE = adverse event; IMP = investigational medicinal product; LOCF = last observation carried forward; MI = multiple imputation; NRI = non-responder imputation; Suppl. = supplementary; TTE = time-to-event.

THIS DOCUMENT CONTAINS CONFIDENTIAL INFORMATION AND MUST NOT BE COPIED OR MADE AVAILABLE TO ANY THIRD PARTY WITHOUT THE PRIOR WRITTEN CONSENT OF THE LEO PHARMA GROUP

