### **Sensitivity analysis**

A sensitivity analysis will be performed for the change and percent change in EASI score from baseline to Week 16 endpoints.

A tipping point analysis will be performed based on implementing a delta-adjusted MI approach. The delta-adjusted imputation approach allows for missing data to be imputed under a MNAR assumption. Heuristically, the imputation strategy, adjusts/shifts the parameters of the MAR distribution based on the value of a numeric offset term, denoted by delta. The tipping point analysis will adjust the values of the parameters in the MAR distribution representing the mean change in EASI score from baseline to Week 16. The analysis will assess how robust the results of the main analysis are to varying departures from the MAR assumption within each treatment group. The range of the shift parameter for the treatment arms will be specified in the SAP along with the seed, the MAR imputation strategy, and the number of imputations.

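### Primary endpoint: Panel 16 imputes values after rescue by MI, Section 11.3.8.1 imputes them by LOCF; the Panel 16 rescue row appears not to have been updated

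*Combined protocol and SAP*

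**What the plan says.** Section 11.3.8.1 sets aside all data after rescue or after permanent discontinuation of IMP, and splits what has to be imputed into two groups. Group 1 covers lack of efficacy, AEs related to worsening AD, and rescue. Its rule is: "The first group will have their missing values imputed using last observation carried forward. This reflects an assumption that subjects that need rescue treatment". The sentence goes on to name subjects who stop IMP for lack of efficacy or worsening AD, and says that none of these subjects can be expected to improve. Group 2 is everything else and is imputed by MI within arm under MAR.

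Panel 16 in Section 11.3.7 is titled as "Handling of observed and missing data according to intercurrent events in the primary analysis of the estimands". For initiation of rescue under the continuous primary estimand, its Observed cell reads "Treated as missing, MI" and its Missing cell reads MI. For discontinuation due to lack of efficacy or worsening AD, the Observed cell reads "Treated as missing, LOCF".

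Section 11.3.6 states that "the hypothesis tests will be based on the analysis of the primary estimand for the primary endpoint". The tipping-point analysis in 11.3.8.1 shifts the MAR imputations: "The delta-adjusted imputation approach allows for missing data to be imputed under a MNAR assumption".

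**The concern.** The two rules give a rescued subject different Week 16 values. MI draws the value from the arm's own model, which in an active arm credits improvement. LOCF holds the last value before rescue and adds no between-imputation variance. The estimate and its standard error therefore both depend on which text the programmer follows, in the analysis that carries the four confirmatory tests.

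The choice also decides who is in the delta-adjusted set. Under Panel 16, rescued subjects are among the MAR-imputed values that delta shifts; under 11.3.8.1 they are not. Finally, group 1 is worded only for values that are set to missing. A value never collected after rescue has no clear rule in 11.3.8.1, whereas Panel 16 assigns it MI.

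**Working it through.** **Texts side by side (continuous primary estimand)**

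| Event | Panel 16 | Section 11.3.8.1 |
|---|---|---|
| Rescue, value observed | MI | LOCF (group 1) |
| Rescue, value missing | MI | not explicit; LOCF by its rationale |
| IMP stopped, lack of efficacy or worsening AD | LOCF | LOCF |
| IMP stopped, other reason | MI | MI (group 2) |

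Only the rescue row disagrees. Group 1 alone might be read as discontinuation caused by rescue, but its rationale lists needing rescue as an alternative to discontinuing. Section 6.5 also keeps subjects on TCS/TCI rescue from Week 4 on IMP, so the two events are distinct. Section 11.3.9.1 again groups rescue with lack of efficacy.

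**Per-subject gap.** Inputs: Panel 14 means; variance 111.0 and covariance 32.5 (Section 11.1). Take a deliberately extreme subject with zero change at all six visits through Week 8. The model mean at Week 16 is

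m16 − (sum of the six earlier means) × 32.5 / (111.0 + 5 × 32.5), with denominator 273.5.

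- Regimen 1: −20.7 + 86.6 × 32.5/273.5 = −10.41
- Regimen 4: −10.0 + 41.6 × 32.5/273.5 = −5.06
- Placebo: −3.5 + 23.7 × 32.5/273.5 = −0.68

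At an assumed baseline EASI of 30 these are −34.7%, −16.9% and −2.3% before bounding to the scale; LOCF gives 0. Divided by 50, each such subject moves the arm mean by 0.69, 0.34 and 0.05 points. The gap differs by arm, so it does not cancel.

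**Trial-level illustration.** From Section 11.1: 5 × 50 subjects, Panel 14 means, the covariance above, bounded changes, and event rates of 20/20/30/40/40% with exponential timing. For the imputation, the plan says: "For each data set, 100 complete versions were generated by imputing missing data separately for each treatment arm". The stated rates are for the "percentage of subjects withdrawing or experiencing an intercurrent event by Week 16 in dose regimens 1-4 and placebo arms", so rescue is not separated from other events. Assumed, because the documents do not give them: baseline EASI lognormal (32/13, truncated to 16-72), no baseline effect, and a rescue share of 50% of events (25-75% in brackets). At 50%, about 5/5/7/10/10 subjects are rescued. There were 1,000 trials with 100 imputations each, ANCOVA on arm and baseline, and Rubin's rules.

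Reproduction with MI throughout: power for regimens 1-4 versus placebo was 100/99.5/96.5/66.5%, against ~100/99.1/97.2/67.4% in Panel 15.

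Replacing only the rescued subjects' Week 16 values by LOCF, regimen 4 versus placebo:

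- Difference: −20.84 (MI) to −18.94 (LOCF), a shift of 1.9 points (1.0-2.8)
- SE: 8.71 to 7.63 (8.2-7.2)
- Mean difference over SE: 20.84/8.71 = 2.39; 18.94/7.63 = 2.48
- Power: 66.5% to 69.0%
- Nominal 5% verdict differs in 12.1% of trials (7.2-15.5%): 4.8% significant only under MI, 7.3% only under LOCF, net 2.5 points

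For regimen 3 the verdict differs in 1.9% (1.0-2.0%), and for regimens 1-2 in at most 0.4%. The regimen 1 difference shrinks by 1.5 points (0.8-2.1) of 50.8.

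If the worst Week 4 responders are rescued, with start after Week 4, the regimen 4 figure is 14.1% (7.6-16.9%) and the regimen 3 figure 2.8% (2.0-4.5%). With baseline 28/12 or 36/14 at a 50% share, regimen 4 gives 10.4% or 11.1% (random) and 15.2% or 14.6% (worst responders). Monte Carlo error is about 1 point.

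**Cross-checks.** A run of 400 trials with 30 imputations, a 50% share and assumed baseline slopes of 0 to −0.7 gave a regimen 4 discordance of 9-11%, with power 59-66% (MI) and 63-68% (LOCF). Another, with 300 trials per scenario, 15 imputations, baseline SD 14 and slope −0.7, gave shifts of 0.7-3.1 points toward zero and power of 36-49% (MI) and 51-67% (LOCF). With MI throughout, that set-up gave only about 43% for regimen 4, so it does not reproduce Panel 15 and its power levels carry little weight. The direction agrees across runs; the size of the power gap does not.

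**The case against.** The strongest reply is that the intended rule can be inferred. Section 11.3.7 presents Panel 16 as an overview, 11.3.8.1 is the operative section and the only one that gives a reason, and 11.3.9.1 repeats its grouping. Section 11.3.1 has the analyses reviewed on blinded data and the SAP finalized before the code is broken, and 11.3.8.1 defers the imputation-model details to the SAP. No SAP text on this is visible in the document supplied, so it may already settle the matter.

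The 12% is also two-way disagreement at the last step of the hierarchy, on an assumed rescue share, and the base case lets rescue start before Week 4. All of this stands. It makes the point a correction rather than a criticism of method. It does not remove the contradiction, because Panel 16's own title claims to state the handling in the primary analysis.

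A reader might infer more than the documents support:

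- That the choice is left wholly open, or could be made after seeing results. The rationale in 11.3.8.1 and the blinded SAP step speak against both.
- That the sample size fails because Section 11.1 describes MI only. In none of the runs was regimen 4 power lower under LOCF.
- That the rescue definition, which stops at items 1-6 of Section 6.7, leaves biologics (item 7) unhandled. Starting one forces permanent IMP discontinuation under 7.2.1, itself an intercurrent event, so later data are excluded. What remains depends on reason coding and is a separate matter.

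**Conclusion.** The contradiction is real, sits in current text, and should be corrected before unblinding. It needs no simulation to establish. The likeliest explanation is that two Panel 16 cells were not brought into line with 11.3.8.1.

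The practical exposure is mainly regimen 4 versus placebo: a shift of about 2 points toward zero, a smaller SE under LOCF, and a different nominal verdict in roughly one trial in eight under the 50% assumption. The exposure for regimen 3 is small and for regimens 1 and 2 negligible. These sizes depend on the assumed rescue share, baseline distribution and baseline effect, none of which the documents give, and should be read as showing that the choice can matter, not how much it will.

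**What to change.** Before unblinding:

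1. In Panel 16, continuous primary estimand, change the rescue row to "Treated as missing, LOCF" (Observed) and LOCF (Missing), matching the lack-of-efficacy row.
2. In 11.3.8.1, say that group 1 also covers values that are missing after the event, not only those set to missing.
3. State whether the delta adjustment applies to group 1.

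The cost is two table cells and one or two sentences, with no change to conduct or data collection. The downside is that LOCF carries no between-imputation variance, so the SE is smaller than under MI and imputation uncertainty for rescued subjects is not reflected. If MI is in fact intended, 11.3.8.1 and its stated rationale would have to change instead.
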